9.9.2 Sample Size and Power for Immunogenicity Analyses

This is a descriptive study and there are no hypotheses to be evaluated. This study will randomize approximately a total of 228 participants into 4 different dose-levels of the V591 group and 57 participants into the placebo group. Table 12 displays the numbers of participants scheduled to receive each study intervention.

Table 12 Numbers of Participants Scheduled to Receive Each Study Intervention

Treatment Group	Number of Participants		
	Day 1 (Dose 1 for all panels)	Day 57 (Dose 2 for Panels A, B, I, and J)	Day 169 (Dose 2 for Panels F [†] , K, and L)
V591-10 ⁴ /10 ⁵ TCID ₅₀	20	0	20
V591-10 ⁵ TCID ₅₀	84	24	20
V591-10 ⁶ TCID ₅₀	84	24	20
V591-10 ⁷ TCID ₅₀	20	0	0
125-fold dilution of V591-10 ⁷ TCID ₅₀	20	0	0
Placebo	57	12	15

TCID₅₀=median tissue culture infectious dose
[†]Participant in Panel F will be administered V591-10⁴ TCID₅₀ or placebo on Day 1, and V591-10⁵ TCID₅₀ or placebo on Day 169.

The width of the 95% CIs for the GMT/GMC ratios depend on the sample size, variability of the natural log concentrations, and the magnitude of the ratio. In Table 13, 95% CIs for various hypothetical GMT/GMC ratios at Day 29 and various hypothetical standard deviation estimates for the natural log titers are displayed. It is assumed that approximately 85% participants will be evaluable for immunogenicity analyses based on PP population at Day 29.

Table 13 95% CIs for Varying Hypothetical GMT/GMC Ratios (V591/Placebo) and Varying Standard Deviations

Standard Deviation of Natural Log Titers/Concentration	GMT/GMC Ratios (V591/Placebo)			
	1.5	2.0	2.5	3.0
1.0	(1.04, 2.17)	(1.38, 2.90)	(1.73, 3.62)	(2.07, 4.34)
1.5	(0.86, 2.61)	(1.15, 3.48)	(1.44, 4.36)	(1.72, 5.23)
2.0	(0.72, 3.14)	(0.95, 4.19)	(1.19, 5.24)	(1.43, 6.29)

CI=confidence interval; GMC=geometric mean concentration; GMT= geometric mean titer.

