Intervention Groups and Duration:

Intervention Groups	Intervention Group Name	Drug	Dose Strength	Dose Frequency	Route of Administration	Vaccination Regimen	Use
	Part 1 (18 to 55 years old) Sentinel Cohort						
	Panel A	V591	1·10 ⁵ TCID ₅₀	2 doses	IM	IM injection on Day 1 and Day 57	Experimental Treatment
	Panel B	V591	1·10 ⁶ TCID ₅₀				
	Panels A, B	Placebo	NA	2 doses	IM	IM injection on Day 1 and Day 57	Placebo
Part 2A (18 to 55 years old)							
	Panel C	V591	1·10 ⁵ TCID ₅₀	Single Dose	IM	Single IM injection on Day 1	Experimental Treatment
	Panel D	V591	1·10 ⁶ TCID ₅₀				
	Panel E	V591	1·10 ⁷ TCID ₅₀				
	Panels C-E	Placebo	NA	Single Dose	IM	Single IM injection on Day 1	Placebo
	Panels F	V591	1·10 ⁴ TCID ₅₀ / 1·10 ⁵ TCID ₅₀	2 doses	IM	IM injection on Day 1 and Day 169	Experimental Treatment
	Panel F	Placebo	NA	2 doses	IM	IM injection on Day 1 and Day 169	Placebo
Part 2B (> 55 years old)							
	Panel G	V591	1·10 ⁵ TCID ₅₀	Single Dose	IM	Single IM injection on Day 1	Experimental Treatment
	Panel H	V591	1·10 ⁶ TCID ₅₀				
	Panels G and H	Placebo	NA	Single Dose	IM	Single IM injection on Day 1	Placebo
	Panel I	V591	1·10 ⁵ TCID ₅₀	2 doses	IM	IM injection on Day 1 and Day 57	Experimental Treatment
	Panel J	V591	1·10 ⁶ TCID ₅₀				
	Panels I and J	Placebo	NA	2 doses	IM	IM injection on Day 1 and Day 57	Placebo
	Panel K	V591	1·10 ⁵ TCID ₅₀	2 doses	IM	IM injection on Day 1 and Day 169	Experimental Treatment
	Panel L	V591	1·10 ⁶ TCID ₅₀				
	Panels K and L	Placebo	NA	2 doses	IM	IM injection on Day 1 and Day 169	Placebo
Abbreviations: IM: intramuscular; NA=not applicable; TCID ₅₀ =Median tissue culture infectious dose							
	Other current or former name(s) or alias(es) for study intervention(s) are as follows: NA						
Total Number of Intervention Groups/ Arms	260 participants (10 in Part 1 younger sentinel cohort, 100 in Part 2A younger cohort and 150 in Part 2B older cohort) will participate in the study that will include a total of 4 dose-levels and 12 Panels. Under each panel, participants will be randomized to receive V591 or placebo in a 4:1 ratio.						

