4.2 Scientific Rationale for Study Design

This study is being conducted to evaluate the safety, tolerability and immunogenicity of V591 in healthy younger (18-55 years of age) and older (> 55 and older) adults. It will probably commence shortly after the Institut Pasteur sponsored FIH clinical study of

V591(also known as TMV-083) in healthy young adults, COVID-19-101, plans to begin. This study is designed to maximize participant safety while permitting efficient trial conduct in the setting of the global COVID-19 pandemic. The design is supported by past clinical and preclinical experience with MV-CHIK which uses the same measles virus vector platform as V591 and has completed Phase 2 trials, as well as preclinical data for V591.

The study consists of a placebo controlled, double-blind, dose-ranging design of single or two doses regimens of V591. The study incorporates two sentinel cohorts to evaluate safety and tolerability of $1 \cdot 10^5$ TCID₅₀ and $1 \cdot 10^6$ TCID₅₀ of V591, doses selected as likely to be immunogenic and well tolerated, before proceeding to additional Panels. Based on prior experience with MV-CHIK immunogenicity, only doses of $V591 \geq 1 \cdot 10^4$ TCID₅₀ will be administered as these are expected to be immunogenic. They have been selected for clinical dosing in order limit the possibility that study participants will being given a sub-immunogenic dose of V591.

MV vector shedding has not been observed in prior clinical study with the MV-CHIK. Vector shedding will be evaluated by PCR in the FIH COVID-19-101 study, and thus it will not be evaluated in this study.

The total sample size was selected to achieve a reasonably sized safety database for the study population exposed to V591. In addition, the sample size is considered to be reasonably sufficient to achieve adequate precision to evaluate the immunogenicity different doses and both single and two regimens of V591.

Overall, this study aims to obtain safety, tolerability and immunogenicity from a broad age range of healthy participants in order to facilitate development of this vaccine.

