
Interim Analyses
	
Up to two interim analyses may be performed on safety and immunogenicity data through at least Day 29. In order to trigger the first interim analysis at least 75% of study participants per Panel in at least 6 Panels must have completed their Day 29 visit. In order to trigger the second interim analysis at least 75% of study participants per Panel in at least 10 Panels must have completed their Day 29 visit.
 
An interim analysis may be performed on safety and immunogenicity data through at least Day 85 for Panels A, B, I, and J. To trigger this interim analysis at least 75% of these Panel’s participants must have completed their Day 85 visit. A minimum percentage of participants from other study Panels is not required for this interim analysis, though all available data will be included.
 
An interim analysis may be performed on safety and immunogenicity data through at least Day 197 for Panels K and L. To trigger this interim analysis at least 75% of these Panel’s participants must have completed their Day 197 visit. A minimum percentage of participants from other study Panels is not required for this interim analysis, though all available data will be included.
 
These interim immunogenicity analyses will include all available nAb PNA and IgG ELISA data.
 
Results of the interim analysis will be provided to the unblinded siDMC.

Multiplicity
	
No multiplicity adjustment is planned.

Sample Size and Power
	
Safety: Section 9.9.1 provides information about the ability of this study to estimate the incidence of AEs within the V591 group as well as differences between V591 and Placebo.
 
Immunogenicity: This is a descriptive study and there are no hypotheses to be evaluated. This study will randomize approximately a total of 208 participants into 4 different dose-levels of the V591 group and 52 participants into the placebo group. Section 9.9.2 provides information about the expected variability of the GMT ratios given the sample size.

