9.9 Sample Size and Power Calculations

9.9.1 Sample Size and Power for Safety Analyses

The probability of observing at least 1 SAE in this study depends on the number of participants vaccinated and the underlying incidence of participants with a SAE in the study population. Calculations below assume that 100% of the randomized participants will be evaluable for safety analyses. There is an 80% chance of observing at least 1 SAE among 228 participants receive a vaccination of V591 if the underlying incidence of a SAE is 0.70%

(1 of every 143 participants receiving the vaccine). There is a 50% chance of observing at least 1 SAE among 228 participants receive a vaccination of V591 if the underlying incidence of a SAE is 0.30% (1 of every 329 participants receiving the vaccine). If no SAEs are observed among the 228 participants receive a vaccination of V591, this study will provide 97.5% confidence that the underlying percentage of participants with a SAE is <1.61% (1 in every 63 participants) in the V591 group.

Table 11 summarizes the percentage point differences between the 2 vaccination groups that could be detected with 80% probability for a variety of hypothetical underlying incidences of an adverse event. These calculations assume 228 participants receive a vaccination of V591 and 57 participants receive placebo and are based on a 2-sided 5% alpha level. The calculations are based on an asymptotic method proposed by Farrington and Manning (1990) [Farrington, C. P. 1990]; no multiplicity adjustments were made.

Table 11 Differences in Incidence of AE Rates between the 2 Vaccination Groups That can be Detected With an ~80% Probability (Assuming 2-sided 5% Alpha Level With 228 Participants in the V591 Group and 57 Participants in the Placebo Group)

Incidence of Adverse Event		Risk Difference
V591 (%)	Placebo (%)	Percentage Points
6.0	0.1	5.9
11.2	2	9.2
16.9	5	11.9
24.9	10	14.9
31.8	15	16.8
38.2	20	18.2
49.9	30	19.9

Incidences presented here are hypothetical and do not represent actual adverse experiences in either group. Based on an asymptotic method [Farrington, C. P. 1990]

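### Section 9.9 is sized on 228 V591 plus 57 placebo, with an arm the design lacks, while the trial randomises 208 plus 52; Table 11 also fails on its own stated inputs

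*Combined protocol and SAP*

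**What the plan says.** The Synopsis (Section 1.1) gives "260 participants (10 in Part 1 younger sentinel cohort, 100 in Part 2A younger cohort and 150 in Part 2B older cohort") in 12 panels, and adds: "Under each panel, participants will be randomized to receive V591 or placebo in a 4:1 ratio". Section 9.1 carries this through as "approximately a total of 208 participants into 4 different dose-levels of the V591 group and 52 participants into the placebo group" and sends the reader to Section 9.9 for the resulting precision.

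Section 9.9.2 instead says "approximately a total of 228 participants into 4 different dose-levels of the V591 group and 57 participants into the placebo group". Table 12 reaches 228 with a fifth active Day 1 row of 20 participants, described as a "125-fold dilution of" the 10^7 TCID50 dose, and with 57 Day 1 placebo.

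Section 9.9.1 uses the same totals. It states: "There is an 80% chance of observing at least 1 SAE among 228 participants receive a vaccination of V591" at an incidence of 0.70%. It also gives a 50% chance at 0.30% and an upper bound of 1.61% if no SAE is seen. Table 11 is headed as 228 V591 against 57 placebo, two-sided 5%, about 80% probability. Table 13 gives confidence intervals for V591/placebo ratios at Day 29, assuming about 85% evaluable, without saying which V591 group is meant.

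Section 4.2 calls the sample size "reasonably sufficient to achieve adequate precision to evaluate the immunogenicity different doses and both single and two regimens" of V591.

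**The concern.** Both totals are current text, and they describe different trials. Safety is the primary objective, and Section 4.2 rests the sample size on the size of the safety database. Section 9.9.1 is where a reader learns what that database can detect, and it answers for 20 more vaccine recipients than the design contains. A 20-person arm that appears only in a sample-size table also leaves doubt about whether a panel was dropped or never existed.

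Table 11 is the plan's only statement of which adverse-event differences the trial could detect. If it does not follow from its own heading, its sensitivity is misdescribed whichever total is right. Anyone quoting Section 9.9 in the study report would carry these figures forward.

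**Working it through.** **Design total.** Tables 3 and 4: Panels A and B have 4 + 1 each; Panels C to L (ten panels) have 20 + 5 each.
- V591: 2×4 + 10×20 = 208. Placebo: 2×1 + 10×5 = 52. Sum 260.
- Table 12, Day 1: 20 + 84 + 84 + 20 + 20 = 228 V591 and 57 placebo, sum 285. Without the dilution row the active total is 208. At 4:1 that row implies 5 placebo, and 57 − 5 = 52. The other active Day 1 rows and the Day 57 and Day 169 columns agree with the 12 panels.
- Section 9.9.2 speaks of four dose levels, but Table 12 beneath it lists five active Day 1 rows.

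**SAE figures.** P(at least one) = 1 − (1 − p)^n. Incidence for a given probability P: 1 − (1 − P)^(1/n). Zero-event bound: 1 − 0.025^(1/n). Section 9.9.1 assumes 100% evaluable.

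| Quantity | Stated | n = 228 | n = 208 |
|---|---|---|---|
| P(≥1 SAE) at 0.70% | 80% | 79.8% | 76.8% |
| P(≥1 SAE) at 0.30% | 50% | 49.6% | 46.5% |
| Incidence for 80% | 0.70% | 0.70% | 0.77% (1 in 130) |
| Incidence for 50% | 0.30% | 0.30% | 0.33% (1 in 301) |
| Bound after zero SAEs | 1.61% | 1.605% | 1.76% (1 in 57) |

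The stated figures belong to n = 228.

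**Table 11.** Normal-approximation power with pooled variance under the null, which is the Farrington and Manning test at a null difference of zero: power = Φ[(d − 1.96·SE0)/SE1]. Here d is the difference, SE0 uses the sample-size-weighted pooled rate, and SE1 uses the two separate rates.

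Example, 38.2% against 20%:
- 228 V591, 57 placebo: pooled rate 0.3456, SE0 = 0.0704, SE1 = 0.0620. (0.182 − 1.96×0.0704)/0.0620 = 0.71, power 76%.
- 57 V591, 228 placebo: pooled rate 0.2364, SE0 = 0.0629, SE1 = 0.0696. (0.182 − 1.96×0.0629)/0.0696 = 0.84, power 80%.

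| Placebo % | Stated difference (points) | Power at stated pair, 228/57 | Power, reversed 57/228 | Detectable difference, 228/57 | Detectable difference, 208/52 |
|---|---|---|---|---|---|
| 0.1 | 5.9 | 42% | 80% | 9.4 | 10.2 |
| 2 | 9.2 | 61% | 80% | 11.7 | 12.5 |
| 5 | 11.9 | 67% | 80% | 14.0 | 14.8 |
| 10 | 14.9 | 72% | 80% | 16.4 | 17.3 |
| 15 | 16.8 | 74% | 80% | 18.0 | 18.9 |
| 20 | 18.2 | 76% | 80% | 19.1 | 20.1 |
| 30 | 19.9 | 78% | 80% | 20.3 | 21.3 |

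Unweighted-pooled, unpooled and one-sided variants with 228/57 do not give 80% across the rows either. Reversing the arms matches all seven differences. In the 0.1% row the arm order accounts for 9.4 − 5.9 = 3.5 points and the change to 208/52 for 10.2 − 9.4 = 0.8. In the 30% row the two parts are 0.4 and 1.0. The normal approximation is poor in the 0.1% row: enumeration gives 37% power for 228/57 there, against 42% above.

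**Table 13.** Interval = ratio × exp[± t(n1 + n2 − 2) × SD × √(1/n1 + 1/n2)]. At ratio 2.0, SD 1.0 (stated 1.38, 2.90):
- 85% of 228 and 57 (194 vs 48): half-width 1.970×0.1612 = 0.318, giving (1.46, 2.75). This does not match.
- 85% of 84 and 57 (71 vs 48): 1.980×0.1869 = 0.370, giving (1.38, 2.90). All 24 printed limits match.
- 85% of 84 and 52 (71 vs 44): 1.981×0.1919 = 0.380, giving (1.37, 2.92).
- 85% of 20 and 52 (17 vs 44): 2.001×0.2856 = 0.571, giving (1.13, 3.54).

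Correcting placebo widens the log half-width by 0.380/0.370 − 1 = 2.7%. A 20-person dose level has a half-width 0.571/0.370 = 1.54 times the one shown.

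**The case against.** The strongest defence is that little depends on these numbers. The plan calls itself descriptive with no hypotheses, Section 9.1 already carries 208 and 52, the SAE probabilities move by about three percentage points, and Amendment 04 ends the study on immunogenicity data. That stands, and it limits the severity. It does not make the two totals compatible. The word approximately does not explain a gap of exactly one panel (20 + 5), and Section 8.11.6 lets panels be omitted or shrunk, which cannot supply an extra arm.

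A reader might infer more than the documents support, in four ways.

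- **That Tables 11 to 13 are all overstated because of 228/57.** In Table 12 only the dilution row and the Day 1 placebo count are wrong. Table 11's larger error in the low-incidence rows is the arm order, so swapping in 208/52 without checking the order would not repair it.
- **That Table 13 is built on 285 participants.** It is not. It inherits only 57 placebo in place of 52. Pooling all 208 against 52 at 85% would give narrower intervals than those printed, such as (1.08, 2.09) against (1.04, 2.17) at ratio 1.5, SD 1.0.
- **That 71 vs 48 is proven as the source of Table 13.** Other pairs, such as 172 vs 34, 201 vs 33 and 245 vs 32, also match every printed limit. The inference rests on 84 and 57 both standing in Table 12.
- **That the plan promises this precision at Day 85 or Day 197.** Table 13 and its 85% assumption are limited to Day 29, and Section 4.2 makes only a general statement. Showing later visits would be an improvement, not a correction.

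**Conclusion.** Section 9.9 does not describe the trial set out in Tables 1, 3 and 4 and Section 9.1. For 208 V591 recipients, all evaluable, the SAE statements are modestly too favourable: 76.8% and 46.5% in place of 80% and 50%, and a zero-event bound of 1.76% in place of 1.61%.

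Table 11 does not follow from its stated arm sizes. True power at its pairs is 42% to 78% for 228/57, and 36% to 74% for 208/52. That the arms were reversed is inferred from an exact match in all seven rows; the plan does not show the calculation.

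Table 13 changes very little with the right placebo count. Its real weakness is the missing label: it appears to apply to a dose level with 84 participants, not to the 10^4/10^5 or 10^7 groups of 20.

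The documents do not show where the dilution row came from. The point is a should-fix: stated precision and internal consistency are affected, but no test, stopping rule or analysis is.

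**What to change.** Reconcile Section 9.9 with Section 9.1, on the basis that the 12-panel design stands:

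1. In Section 9.9 and Table 12, set V591 to 208 and Day 1 placebo to 52, and delete the dilution row. Leave the Day 57 and Day 169 columns as they are.
2. Restate the SAE figures as 0.77% (1 in 130) for an 80% chance, 0.33% (1 in 301) for a 50% chance, and below 1.76% (1 in 57) if none is seen.
3. Recompute Table 11 with 208 V591 and 52 placebo in the labelled order. The detectable differences are about 10.2, 12.5, 14.8, 17.3, 18.9, 20.1 and 21.3 points. Use an exact method for the 0.1% row, or add a caution there.
4. Recompute Table 13 at 71 vs 44 and label it as the 10^5 or 10^6 dose level against pooled placebo at Day 29.
5. Optional: add rows for the 20-person dose levels, Day 85 and Day 197. If added, use one stated evaluability assumption throughout, and describe the 10 placebo at Day 197 as Panels K and L pooled (5 each).

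The cost is a text correction and three revised tables, with somewhat less favourable figures. Enrolment, data collection and analysis methods do not change.

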10 SUPPORTING DOCUMENTATION AND OPERATIONAL CONSIDERATIONS

10.1 Appendix 1: Regulatory, Ethical, and Study Oversight Considerations

10.1.1 Code of Conduct for Clinical Trials

Merck Sharp and Dohme Corp., a subsidiary of Merck & Co., Inc. (MSD)

Code of Conduct for Interventional Clinical Trials

I. Introduction

A. Purpose

MSD, through its subsidiaries, conducts clinical trials worldwide to evaluate the safety and effectiveness of our products. As such, we are committed to designing, implementing, conducting, analyzing, and reporting these trials in compliance with the highest ethical and scientific standards. Protection of participants in clinical trials is the overriding concern in the design and conduct of clinical trials. In all cases, MSD clinical trials will be conducted in compliance with local and/or national regulations (including all applicable data protection laws and regulations), and International Council for Harmonisation Good Clinical Practice (ICH-GCP), and also in accordance with the ethical principles that have their origin in the Declaration of Helsinki.

B. Scope

Highest ethical and scientific standards shall be endorsed for all clinical interventional investigations sponsored by MSD irrespective of the party (parties) employed for their execution (e.g., contract research organizations, collaborative research efforts). This Code is not intended to apply to trials that are observational in nature, or which are retrospective. Further, this Code does not apply to investigator-initiated trials, which are not under the full control of MSD.

II. Scientific Issues

A. Trial Conduct

1. Trial Design

Except for pilot or estimation trials, clinical trial protocols will be hypothesis-driven to assess safety, efficacy and/or pharmacokinetic or pharmacodynamic indices of MSD or comparator products. Alternatively, MSD may conduct outcomes research trials, trials to assess or validate various endpoint measures, or trials to determine patient preferences, etc.

The design (i.e., participant population, duration, statistical power) must be adequate to address the specific purpose of the trial and shall respect the data protection rights of all participants, trial site staff and, where applicable, third parties. Participants must meet protocol entry criteria to be enrolled in the trial.

2. Site Selection

MSD selects investigative sites based on medical expertise, access to appropriate participants, adequacy of facilities and staff, previous performance in clinical trials, as well as budgetary considerations. Prior to trial initiation, sites are evaluated by MSD personnel (or individuals acting on behalf of MSD) to assess the ability to successfully conduct the trial.

3. Site Monitoring/Scientific Integrity

Investigative trial sites are monitored to assess compliance with the trial protocol and Good Clinical Practice (GCP). MSD reviews clinical data for accuracy, completeness, and consistency. Data are verified versus

source documentation according to standard operating procedures. Per MSD policies and procedures, if potential fraud, scientific/research misconduct, privacy incidents/breaches or Clinical Trial-related Significant Quality Issues are reported, such matters are investigated. When necessary, appropriate corrective and/or preventative actions are defined and regulatory authorities and/or ethics review committees are notified.

B. Publication and Authorship

Regardless of trial outcome, MSD commits to publish the primary and secondary results of its registered trials of marketed products in which treatment is assigned, according to the pre-specified plans for data analysis. To the extent scientifically appropriate, MSD seeks to publish the results of other analyses it conducts that are important to patients, physicians, and payers. Some early phase or pilot trials are intended to be hypothesis-generating rather than hypothesis testing; in such cases, publication of results may not be appropriate since the trial may be underpowered and the analyses complicated by statistical issues such as multiplicity.

MSD's policy on authorship is consistent with the recommendations published by the International Committee of Medical Journal Editors (ICMJE). In summary, authorship should reflect significant contribution to the design and conduct of the trial, performance or interpretation of the analysis, and/or writing of the manuscript. All named authors must be able to defend the trial results and conclusions. MSD funding of a trial will be acknowledged in publications.

III. Participant Protection

A. Regulatory Authority and Ethics Committee Review (Institutional Review Board [IRB]/Independent Ethics Committee [IEC])

All protocols and protocol amendments will be submitted by MSD for regulatory authority acceptance/authorization prior to implementation of the trial or amendment, in compliance with local and/or national regulations.

The protocol, protocol amendment(s), informed consent form, investigator's brochure, and other relevant trial documents must be reviewed and approved by an IRB/IEC before being implemented at each site, in compliance with local and/or national regulations. Changes to the protocol that are required urgently to eliminate an immediate hazard and to protect participant safety may be enacted in anticipation of ethics committee approval. MSD will inform regulatory authorities of such new measures to protect participant safety, in compliance with local and/or national regulations.

B. Safety

The guiding principle in decision-making in clinical trials is that participant welfare is of primary importance. Potential participants will be informed of the risks and benefits of, as well as alternatives to, trial participation. At a minimum, trial designs will take into account the local standard of care.

All participation in MSD clinical trials is voluntary. Participants enter the trial only after informed consent is obtained. Participants may withdraw from an MSD trial at any time, without any influence on their access to, or receipt of, medical care that may otherwise be available to them.

C. Confidentiality

MSD is committed to safeguarding participant confidentiality, to the greatest extent possible, as well as all applicable data protection rights. Unless required by law, only the investigator, Sponsor (or individuals acting on behalf of MSD), ethics committee, and/or regulatory authorities will have access to confidential medical records that might identify the participant by name.

D. Genomic Research

Genomic research will only be conducted in accordance with a protocol and informed consent authorized by an ethics committee.

IV. Financial Considerations

A. Payments to Investigators

Clinical trials are time- and labor-intensive. It is MSD's policy to compensate investigators (or the sponsoring institution) in a fair manner for the work performed in support of MSD trials. MSD does not pay incentives to enroll participants in its trials. However, when enrollment is particularly challenging, additional payments may be made to compensate for the time spent in extra recruiting efforts.

MSD does not pay for participant referrals. However, MSD may compensate referring physicians for time spent on chart review and medical evaluation to identify potentially eligible participants.

B. Clinical Research Funding

Informed consent forms will disclose that the trial is sponsored by MSD, and that the investigator or sponsoring institution is being paid or provided a grant for performing the trial. However, the local ethics committee may wish to alter the wording of the disclosure statement to be consistent with financial practices at that institution. As noted above, all publications resulting from MSD trials will indicate MSD as a source of funding.

C. Funding for Travel and Other Requests

Funding of travel by investigators and support staff (e.g., to scientific meetings, investigator meetings, etc.) will be consistent with local guidelines and practices.

V. Investigator Commitment

Investigators will be expected to review MSD's Code of Conduct as an appendix to the trial protocol, and in signing the protocol, agree to support these ethical and scientific standards.

